6.2 Duration of the study

It is a cross-sectional study. The duration of the study is so long that all participants are recruited and examined.

6.3 Selection of study participants

Inclusion criteria for participants without hypoglycemia unawareness

- Age between ≥ 18 and ≤ 75 years
- BMI between 20 und 35 kg/m²
- Persons with manifest diabetes mellitus type 1 and diagnosis according to DDG guidelines 2011 oGTT, HbA1c $\geq 6.5\%$ in the absence of adulteration of the HbA1c, over 200 mg / dl in the 2 hour value of the oGTT, fasting glucose > 126 mg/dl, spontaneous glucose > 200 mg/dl at least twice).

Inclusion criteria for participants without hypoglycemia unawareness

- Persons who are not aware of hypoglycemia symptoms at glucose levels above 50 mg / dl
- Age between ≥ 18 and ≤ 75 years
- BMI between 20 und 35 kg/m²
- Persons with manifest diabetes mellitus type 1 and diagnosis according to DDG guidelines 2011 oGTT, HbA1c $\geq 6.5\%$ in the absence of adulteration of the HbA1c, over 200 mg / dl in the 2 hour value of the oGTT, fasting glucose > 126 mg/dl, spontaneous glucose > 200 mg/dl at least twice).

General exclusion criteria

- Secondary types of diabetes (ADA-criteria type 3 B-H)
- Current pregnancy
- Acute infections / fever
- Immune-suppressant therapy
- Severe psychiatric diseases requiring treatment (for example personality disorders, schizophrenia, depression)
- Known alcohol or drug dependency
- Severe heart-, kidney-, or liver-insufficiency:
 - NYHA stadium IV
 - Non-diabetic liver disease (for example PBC, PSC, Wilson's disease, hemochromatosis, autoimmune hepatitis)

- severe peripheral artery disease (stadium IV)
- non-diabetic glomerulopathy
- Cancer or other malignant diseases within the last 5 years
- Infectious diseases like hepatitis B, C, E, or HIV
- Other severe autoimmune diseases
- Current participation in an interventional study
- Anemia or disorders of bone marrow
- **Exclusion criteria for clamp study:**
 - Past history of deep vein thrombosis or pulmonary embolism
 - Routine laboratory test results $\leq 80\%$ below lower reference value: Ferritin, iron, leucocytes, haemoglobin, hematocrit, RBC, platelets, blood alcohol levels.
- **Exclusion criteria for bioimpedance measurement:**
 - Pacemaker / ICD
- **Exclusion criteria for lung function testing:**
 - Ignoring or non-understanding of the instructions

6.4 Course of the study

One day is scheduled for basic testing. Study participants are scheduled to arrive between 11 and 12 am in a fasting state. The basic examinations take three to four hours, dependent on the total number of patients in the outpatient clinic since some devices have to be shared with clinical routine. QST takes 90 minutes and can be performed on the same day as basic testing. On a second day a hyperinsulinemic clamp examination is performed, which will be scheduled separately, within four weeks of basic testing. The clamp lasts about 5 hours including the follow-up time. Initially blood is drawn in order to measure of plasma glucose, Asprosin, insulin, C-peptide, adrenaline, norepinephrine, glucagon and cortisone concentrations, and twice for the biobank (at the beginning and end of the test) and for determining the values of the routine lab testing will be performed. In addition, a urine examination takes place. All tests will be performed according to SOPs by trained personnel. All participants are informed of the driving prohibition for the rest of the day after enduring the Clamp test.

6.5 Potential complications and risks

This study will yield new data on the new hormone asprosin und the Pathomechanism of the hypoglycaemia unawareness. Under consideration of the limitations, we strive to identify different subgroups of type 1 diabetics with or without hypoglycaemia unawareness, which would

be separated on the basis of combinations of specific biomarkers and genetic characteristics and therefore bear either a high or a low risk for the development of diabetes-associated complications. This could have an impact on and direct consequences for specific differential therapies and specific preventive strategies. Expected medical complications are rather rare and only mild. In case of venous blood draws and placement of iv-cannulas, there is a risk for hematomas, infections, and very rarely phlebitis or thrombophlebitis. Even rarer is a temporary or even permanent damage of small nerve fibers in the skin.

In the clamp study, total blood volume will not exceed 270 ml including blood for the biobank. . This volume is the equivalent of half a blood donation, which is usually well tolerated, so that the total amount of blood drawn should not real to complications.

All stimuli applied during the QST are close to the pain threshold and therefore tolerable for the study participants. Moreover, study participants have the possibility to abort the test at any time point. Painful stimuli can lead to a slight temporary local flush of the skin.

During optional clamp testing, hypoglycemia can occur during or shortly afterwards. Moreover, hypokalemia can occur due to simultaneous infusion of insulin and glucose. Both complications can be treated immediately and effectively by supplementation of glucose (which is always running anyway) and oral supplementation of potassium, respectively.

6.6 Stopping criterion

The only reason is for a study participant to withdraw from study participation. In this cross-sectional study is that not to be expected.

6.7 Concomitant therapy

The study does not influence the study participants' regular medication of other medical treatment in any way.

7. Statistical analysis and sample size calculation

The number of 10 subjects suffices for this pilot project. The aim of the study is to assess the asprosin effect during the hyperinsulinemic clamp test as well as its correlation to the rest of

Asprosin dynamics relating to serum Glucose levels under controlled alteration from Version 1.1 Stand 31.05.17

known regulatory hormones. Because of the low number of participants, only non-parametric evaluations, as well as descriptive and graphical statements, are used. Depending on the parameter, relating or non-relating non-parametric tests are performed. It is a pilot study in which no large statistical calculations are possible or, currently necessary. No biometrics will be involved in the evaluation.

The effect variables determined in this study, in particular asprosin kinetics under different glucose related metabolism conditions, can be further used for possible power analysis of larger future studies.

8. Data collection and data management

All collected data from the study will be transferred into a case report form (CRF), which contains an unequivocal participation number. Moreover, all samples will be labeled with a code number, so that all analyzes can be performed by use of a pseudonym. Questionnaires containing personal data will be stored separately. The code can only be associated with the study participant by a small group of direct employees of the Study Center for Diabetes Research of the University of Heidelberg. Decoding only takes place in case of withdrawal from study participation in order to erase all data, or in case of severe medical findings about which the study participant has to be informed. In statistical analyses and publications, data will be completely anonymous. Anonymization will be performed during creation of excel sheets of SPSS tables, which do not contain a pseudonym anymore. All data and results from the study are subject to professional secrecy. Results in the context of medical publications will only be presented as statistical entities. Study files will be stored in a lockable room, which can only be accessed by employees of the Study Center for Diabetes Research of the University of Heidelberg. Clinical data will be stored for 15 years.

Moreover, a biobank will be created. Samples will be stored at -80°C in designated freezers up to 5 years, labeled by use of pseudonyms. The pseudonym is the same used for clinical data. From material stored in the biobank, different analyses associated with glucose metabolism are planned, especially concerning the regulation of different pathways, production and concentrations of reactive dicarbonyls, as well as the analysis of reactive oxygen species. Specific scientific questions, however, cannot be appointed at this point. Therefore, we reserve the right to perform other analyses, for example in case alternative substances or metabolic pathways are detected during the running period of the study.

Electronic documentation of the data will be performed using a Microsoft Access® database (Microsoft Deutschland GmbH, Unterschleißheim), which has been created locally in Heidelberg. Database hosting including backups will take place at the office of the Clinical Study Center for Diabetes Research of the University of Heidelberg, Department Medicine I. Data will be stored on an external hard drive, with backup on a second external hard drive. For encryption of the data, a pseudonym will be used. Data will only be accessed and used by employees of the Clinical Study Center for Diabetes Research of the University of Heidelberg. The external hard drives will be stored secured in the office of the Clinical Study Center for Diabetes Research of the University of Heidelberg, to which only a small group of employees in this study center have access. Data will be stored electronically as described, a CRF on paper is only planned for emergencies (power failures) and for parts of the questionnaires that have to be filled in by the study participants themselves.

9. Legal regulations and insurance

All study examinations will be performed according to the medical professional act and in accordance to the Declaration of Helsinki (2013).

All study participants will be informed about the aims of the study, the conduction of the diagnostic tests and the blood draw, as well as the risks associated with them before enrollment by the study doctor. The patient is enrolled in the study after obtaining written informed consent. Study participation is completely voluntary, and study participants can withdraw from study participation any time without specific reasons and without negative consequences concerning future medical care. In case of withdrawal, study participants can decide whether their biomaterial will be destroyed or can be used anonymously for ongoing medical research. The names of the study participants, as well as all other confidential data are subject to medical confidentiality and regulations of the German Federal Data Protection Act. Personal data will only be passed on by use of a pseudonym, and only in case specific analyses using biomaterial cannot be performed at the University of Heidelberg due to technical or organizational reasons. In that case, material can be sent to other research facilities. This is specifically explained in the information form for study participants, which will be handed to every person interested in participation before enrollment. Third parties will not get access to original data and files.

Compensation insurance for accidents en route has not been contracted.

Heidelberg, 31/05/2017

[name]
Head of the Clinical Study Center for Diabetes
Research
University Hospital Heidelberg

Asprosin dynamics relating to serum Glucose levels under controlled alteration

Statistical Analysis Plan

Heidelberg, 31/05/2017

Statistical analysis and sample size calculation

The number of 10 subjects suffices for this pilot project. The aim of the study is to assess the asprosin effect during the hyperinsulinemic clamp test as well as its correlation to the rest of known regulatory hormones. Because of the low number of participants, only non-parametric evaluations, as well as descriptive and graphical statements, are used. Depending on the parameter, relating or non-relating non-parametric tests are performed. It is a pilot study in which no large statistical calculations are possible or, currently necessary. No biometrics will be involved in the evaluation. For evaluating differences in asprosin concentrations during different time points of the clamp, Wilcoxon test will be used. For correlations between asprosin concentration and blood glucose concentration, Kendall-tau test will be used. For ruling out confounders, linear regression analysis will be performed. For descriptive analysis, median and range will be given. As software, IBM SPSS 23.0 will be used.

The effect variables determined in this study, in particular asprosin kinetics under different glucose related metabolism conditions, can be further used for possible power analysis of larger future studies.

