2.2 Study coordination and study doctors

[name] (study doctor)

Internal Medicine I and clinical chemistry

Medical faculty of the University hospital Heidelberg

[name]

[name]

Phone: [name], fax [name]

[name] (study doctor)

Specialist for Internal Medicine

Internal Medicine I and clinical chemistry

Medical faculty of the University hospital Heidelberg

[name]

[name]

Phone: [name], fax [name]

[contact]

3. Summary

The Pilot study entitled „ Asprosin Dynamics relating to serum Glucose levels under controlled alterations“ is designed to date the asprosin kinetics at various metabolic states relating to serum glucose and the correlation between asprosin and the known glucose-regulating hormones.

Asprosin is the C-terminal cleavage product of profibrillin. This new hormone is encoded by FBN1 Gen (Amino acid residues 2732-2871, molecular weight 30 kDa), which also encodes fibrillin. The hormone was initially discovered during the analysis of the genome of patients with the extremely rare Wiedemann- Rautenstrauch - syndrome (Romere C. et al 2016 Cell). According to the data so far, asprosin is a fast- induced protein hormone that acts on the liver through cell membrane receptors, where it activates the G protein cAMP- PKA pathway, leading to a rapid release of glucose into the circulation and to compensatory insulin production. The above seems to match the constellation found in overweight type 2 diabetes patients or patients with metabolic syndrome ("insulin resistance"). Diabetic mice were able to normalize their glucose and insulin levels by asprosin-binding antibodies. According to a recent study (Romere C. et al 2016 Cell), asprosin had no influence on the serum concentration of glucagon, epinephrine, nor- epinephrine and cortisol in mice. In humans it is known that asprosin increases during fasting.

The liver- related glucose release into the blood circulation is crucial for the brain function and overall survival during fasting. In addition, a compensatory rise in asprosin is expected during a hypoglycemic episode. In this pilot study, the asprosin concentration is measured both in participants with type 1 Diabetes mellitus, with or without hypoglycemia unawareness during a hypoglycemic phase. These relevant measurements are compared in the two subgroups, consisting of 5 persons each.

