In this pilot study, five people with and five without hypoglycemia unawareness will be recruited and comprehensively phenotyped. The participants will be type 1 diabetics with a BMI between 25 and 35 kg / m² and 18 to 75 years of age. An extensive phenotyping of the participants will be performed, which will bring important new data on type 1 diabetes and diabetes related late complications. What takes place is the characterizing of the participants regarding their Asprosin

levels when fasting and after glucose or insulin administration (hyperinsulinemic Clamp test) as well as of the diabetic late complications even in the subgroups that form. Eventually, the correlation of the asprosin serum concentration against the other regulating hormones such as glucagon, catecholamine and cortisol will be thoroughly evaluated. A platform for discussion is created in this way, one that can still not be reached through current studies.

This is to be the first study of its kind, in which plasma levels of asprosin is determined and Type 1 diabetics with and without hypoglycemia unawareness are thoroughly examined in order to identify possible differences and similarities for the better determination of the new hormone utilizing the framework of hyperinsulinemic Clamp- Tests. The intention behind is to better understand the (patho-) physiology of the hypoglycaemia unawareness, as well as to better characterize the physiological properties of asprosin.

5. Aims and hypotheses of the study

The following hypotheses shall be studied:

- Asprosin, as fast- induced protein hormone, increases serum levels in type 1 diabetics with or without diabetes late- complications during a hypoglycemic phase.
- Asprosin increases serum levels more significantly in diabetics without hypoglycemia unawareness compared to diabetics with hypoglycemia unawareness.
- There is probably no correlation between asprosin and the previous known regulating hormones.

In order to investigate these hypotheses, study participants will be initially profoundly examined in our Clinical Study Center regarding both their glycemic metabolic responses and the clinical findings relating to their possible micro- and macrovascular complications. In addition to this quality of life, well-being, depression and neuropathic pain is going to be taken into account.

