People interested in study participation can contact the Clinical Study Center via phone or e-mail. Written information will be sent by post or handed out directly. At a separate appointment, oral and written informed consent will be obtained by a study doctor, so that study participants have enough time to think.

Basic testing will take one day. On the first day are planned various non-invasive clinical routine examinations. Study participants will be invited between 10 and 12 a.m. starving. The basic tests take three to four hours, depending on the number of study participants invited on that day. Quantitative sensor testing takes approximately 90 minutes of additional time, it will be take place on the first day too. On a second day a hyperinsulinemic clamp examination is performed, which will be scheduled separately, within four weeks of basic testing.

The clamp lasts about 5 hours including the follow-up time. Initialy blood is drawn in order to measure of plasma glucose, Asprosin, insulin, C-peptide, adrenaline, norepinephrine, glucagon and cortisone concentrations, and twice for the biobank (at the beginning and end of the test) and for determining the values of the routine lab testing will be performed. In addition, a urine examination takes place. All tests will be performed according to SOPs by trained personnel.

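### The SAP limits itself to non-parametric methods because the sample is small, then adds a linear regression to rule out confounders, which ten non-randomised persons cannot deliver

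*SAP*

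**What the plan says.** The SAP's single section (Statistical analysis and sample size calculation) sets the restriction and its reason: "Because of the low number of participants, only non-parametric evaluations, as well as descriptive and graphical statements, are used". It adds that "Depending on the parameter, relating or non-relating non-parametric tests are performed". It then names a Wilcoxon test for asprosin across clamp time points and Kendall's tau for asprosin against blood glucose. Next comes the sentence at issue: "For ruling out confounders, linear regression analysis will be performed". No exception to the restriction is made for it. The SAP does not name the outcome, the exposure, the covariates or the unit of analysis, and it does not say what result would count as ruling a confounder out.

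Section 7 of the protocol contains the same restriction and no regression, so the conflict arises from text that only the SAP has.

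On design, section 3 of the protocol says of the hypoglycemic-phase measurements: "These relevant measurements are compared in the two subgroups, consisting of 5 persons each". The groups are formed by an existing characteristic. In section 6.3 the criterion that separates them is "Persons who are not aware of hypoglycemia symptoms at glucose levels above 50 mg / dl". No random assignment is described, and section 6.2 calls the study cross-sectional.

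**The concern.** There are two problems. First, a linear regression with an inferential purpose is not a non-parametric, descriptive or graphical method. An analyst who follows one sentence of the SAP breaks the other.

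Second, the purpose promises more than the design can give. Confounding is a live matter here. Section 4 of the protocol says that asprosin comes mainly from white adipose tissue and is raised in insulin resistance. Section 6.3 admits ages 18 to 75 and BMI 20 to 35 kg/m², and no matching is described. Two groups of five could easily differ on such traits. If the report says that confounders were ruled out by regression, readers will trust a group difference or a correlation more than ten persons allow.

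**Working it through.** **What can be reproduced.** Nothing numerical. The plan gives 10 subjects (5 + 5) without alpha, power, effect size or standard deviation. The figures below illustrate the point under stated assumptions.

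**Inputs from the documents.** Ten persons; two groups of five; groups defined by an existing trait.

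**Assumed.** Two-sided 0.05; normal data; one value per person; one exposure plus one covariate; and, for steps 1 to 3 only, a rule that a non-significant covariate is taken as excluded.

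**Step 1: what the covariate must reach.** Residual degrees of freedom = 10 − 3 = 7 (intercept, exposure, covariate). The critical t is 2.365. The critical partial correlation is t / √(df + t²) = 2.365 / √(7 + 5.59) = 0.67.

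**Step 2: what a null finding would leave open.** For an observed partial correlation of 0, the 95% interval by Fisher's z is ± tanh(1.96 / √(10 − 1 − 3)) = ± tanh(0.80) = ± 0.66. A covariate that shows no association at all in the sample would still be compatible with a strong one.

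**Step 3: how often a real confounder would look absent.** Simulation of 5 v 5 with no true group effect: covariate z differs by 1 SD between groups, and y = b·z + √(1 − b²)·e. The model contains group and z.

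| Partial correlation b | z non-significant |
|---|---|
| 0.3 | 88% |
| 0.5 | 71% |
| 0.7 | 38% |

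A continuous exposure in place of group gives the same percentages, so this step does not depend on which exposure the SAP has in mind.

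**Step 4: what adjustment does achieve.** Same simulation, now looking at the group effect.

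| b | Unadjusted bias (SD) | Adjusted bias (SD) | False positives, unadjusted | False positives, adjusted | Median 95% half-width, adjusted (SD) |
|---|---|---|---|---|---|
| 0.3 | 0.30 | about 0 | 7% | 5% | 1.6 |
| 0.5 | 0.50 | about 0 | 11% | 5% | 1.5 |
| 0.7 | 0.70 | about 0 | 16% | 5% | 1.2 |

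Adjusting for the right measured covariate removes its bias even though that covariate is usually non-significant at 0.3 and 0.5. The adjusted estimate is nevertheless very imprecise.

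**Step 5: unmeasured confounding.** If z (b = 0.5, 1 SD apart) is not measured, the bias is 0.50 SD with 10 persons and still 0.50 SD with 1,000. No sample size removes it.

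**Step 6: where the figures do not apply.** Module 3 in section 6.1 of the protocol describes serial samples in each person. If the regression pools them, 7 residual degrees of freedom is wrong. Dependence within person would then tend to overstate significance, which is a different fault from low power. The Wilcoxon comparisons across clamp time points are also outside these figures: each person is their own control, so fixed personal traits do not confound them.

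**The case against.** The strongest reply is that ruling out may be loose wording for adjusting. The SAP does not say that a covariate will be tested and declared excluded if it is non-significant. A reader might infer such a rule, but neither document states it, so the 88/71/38% describe the consequence of one reading and not a planned procedure. This part of the reply stands. It does not rescue the sentence: under the adjusting reading the stated purpose is still wrong, because adjustment for one measured covariate rules nothing out, and the conflict with the restriction remains.

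A second reply is that a regression could count as a descriptive statement. That would hold for a fitted line shown without inference. It fails here because ruling out is an inference.

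A third is that this is a declared pilot with no confirmatory claim. That limits the consequence to over-interpretation of an exploratory result. It does not justify the wording.

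Other inferences go further than the documents:

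- **The regression serves the 5 v 5 comparison.** The SAP does not tie it to that comparison, so the bias figures in step 4 are conditional on that use.
- **Results should be reported unadjusted only.** The 0.3/0.5/0.7 SD bias belongs to the unadjusted estimate, and step 4 shows that adjustment can remove it.
- **The plan will read a non-significant hormone correlation as absence.** The protocol does hypothesise that "There is probably no correlation between asprosin and the previous known regulating hormones", and the SAP names Kendall's tau only for glucose. But no document says that non-significance will be taken as proof. Section 5 of the protocol also plans to measure glucagon, catecholamines and cortisol during and at the end of the clamp and to correlate them with asprosin. The absence of a named test and interval for each hormone is missing detail and lies outside this point.

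**Conclusion.** The point holds: the sentence is wrong as written. It contradicts the restriction in the SAP and has no counterpart in section 7 of the protocol. It also sets an aim that ten persons in trait-defined groups cannot meet.

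The low-power figures rest on assumptions that the documents do not supply: two-sided 0.05, normality, one value per person, one exposure plus one covariate, and non-significance read as exclusion. They fall away if serial samples are pooled. The conclusion does not depend on them, because unmeasured confounding remains whatever the model or the sample size.

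The finding is not that regression is useless here. One well-chosen adjustment can remove bias from a measured covariate; it cannot show that confounding is absent. For an exploratory pilot this should be corrected, and it does not threaten the study.

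**What to change.** 1. Delete the ruling-out wording. State instead that confounding cannot be excluded in this non-randomised pilot of ten participants, and show candidate confounders by group as median and range.
2. Either drop the regression, or keep it as one model labelled exploratory. If it is kept, name the outcome, the exposure, a single covariate, and one value or change per person before the data are analysed. Report the adjusted estimate with its 95% interval beside the unadjusted result. Do not require unadjusted reporting only.
3. If the regression is kept, amend the restriction to non-parametric methods in the SAP and in section 7 of the protocol so that both allow it.

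Cost: a few sentences in the SAP and, if the regression stays, one in the protocol. No new data or visits are needed. The downside is that the report can no longer claim that confounding was excluded, a claim the data could not have supported.
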